8.4.1 Laboratory evaluations

A central laboratory will be used for analysis of all specimens detailed in this section unless noted otherwise. Details on the collections, shipment of samples and reporting of results by the central laboratory are provided to investigators in the laboratory manual.

Clinically notable laboratory findings are defined in [Section 16.1](#) Appendix 1. In case of lab abnormalities, an additional re-draw for central laboratory assessment is allowed during the screening period to confirm eligibility criteria.

Clinically significant abnormalities must be recorded on the relevant section of the Case report/Record Forms (CRFs) capturing medical history/Current medical conditions/AEs.

A sample for serum β -hCG assessment will be collected at screening Visit 1 for all pre-menopausal women who are not surgically sterile.

Table 8-10 Laboratory Assessments

Test Category	Test Name
Hematology	Hemoglobin, hematocrit, red blood cell count, white blood cell count with differential and platelet count will be measured.
Coagulation	At Visits 1 and 110 coagulation will be assessed by International Normalized Ratio (INR).
Chemistry	Albumin, total bilirubin, alkaline phosphatase, AST, ALT, LDH, GGT, chloride, sodium, potassium, magnesium, calcium, inorganic phosphorus, creatinine, urea/BUN and uric acid will be measured. If the total bilirubin concentration is increased above 1.5 times the upper limit of normal, direct and indirect reacting bilirubin should be differentiated. Serum hCG is assessed at Visit 1 only.
Urinalysis	A midstream urine sample (approximately 30 mL) will be obtained, in order to avoid contamination with epithelial cells and sediments, and allow proper assessments. Semi-quantitative "dipstick" evaluation for specific gravity, glucose, protein, bilirubin, ketones, leukocytes, blood and pH will be performed at site. When a dipstick evaluation is abnormal, eg, positive for WBC and/or blood, a urine sample must be sent to the Central Lab for microscopic examination including RBC and WBC. (Details on collection of urine for analysis by central laboratory are provided to investigators in the laboratory manual.)
Parasite screening	Assessment of stool samples for parasitic infections (refer to Assessment of parasitic infections Section 8.4.3)
Pregnancy Test	Serum / Urine pregnancy test (refer to Pregnancy and assessments of fertility Section 8.4.4). If urine pregnancy test is positive, confirmation by serum β -hCG test should be done by central lab.

WBC: white blood cell(s); RBC: red blood cell(s); LDH: lactate dehydrogenase; GGT: gamma-glutamyl transferase

8.4.2 Electrocardiogram (ECG)

Standard 12 lead ECGs must be recorded after 10 minutes rest in the supine position to ensure a stable baseline. The preferred sequence of cardiovascular data collection during study visits is ECG collection first, followed by vital signs, and blood sampling. The Fridericia QT correction formula (QTcF) should be used for clinical decisions.

Single ECGs will be collected at Visits 1 and Visit 240/End of treatment (EoT)/Sudy Treatment Discontinuation (TD).

The original ECG will be sent electronically to the Clinical Research Organization (CRO) directly from the provided ECG machine. Two "identical" duplicate print-outs will be generated

on non-heat sensitive paper and kept at the investigator site as source documentation and as back-up for submission to the vendor in case of problems with the electronic transmission. The “identical” duplicates must be labeled with study number, subject initials, subject number, date and time, and signed and archived in the study site source documents.

Clinically significant ECG findings prior to dosing with investigational treatment must be discussed with the sponsor. Clinically significant abnormalities must be recorded on the relevant section of the CRFs capturing Medical history/Current medical conditions/AE as appropriate.

Full details of all procedures relating to the ECG collection and reporting will be contained in a technical manual to be provided by the CRO to each investigator site.

For any ECGs with subject safety concerns, 2 additional ECGs must be performed to confirm the safety finding.

8.4.3 Assessment of parasitic infections

All subjects will be given three stool sample collection kits at screening Visit 1 and Visit 320 by the site or site's local laboratory. Subjects will take the stool sample kits home and collect stool samples, from three different bowel movements, ideally on three different days, within seven days of Visit 1 and in the week prior to Visit 1999. Subjects will return the three stool samples to the site as soon as possible after Visit 1 (in order to allow processing within the screening period) and at Visit 1999.

Stool samples for parasitic disease will be examined for ova and parasites by the local laboratory. The identification of organisms in positive stools will be made by local laboratory. If stool testing is positive for pathogenic organisms (pathogenic as defined by the local laboratory), the result must be recorded in the eCRF and the subject will not enter treatment period and will not be allowed to rescreen. Stool samples negative for pathogenic organisms must be recorded in the eCRF before Visit 110.

Subjects must be advised that if diarrhea, or any other symptoms suggestive of parasitic infection, develops at any time before the end of study, three additional stool samples must be collected at next visit or sooner and sent to local laboratory for analysis.

8.4.4 Pregnancy and assessments of fertility

All pre-menopausal women who are not surgically sterile will have sample for serum β -hCG test collected at screening Visit 1. Post-menopausal status should be recorded in the CRF.

At Visit 110 and subsequent study visits until Visit 1999/EOS/PSD, all pre-menopausal women who are not surgically sterile will have urine pregnancy testing performed BEFORE administration of the study medication. A positive urine test needs to be confirmed with a central lab serum test prior to study drug administration. If positive, the subject must be discontinued from study treatment.

Additional pregnancy testing might be performed if requested by local regulatory/ethics committee requirements.

Assessments of fertility

Medical documentation of oophorectomy, hysterectomy, or tubal ligation must be retained as source documents. Subsequent hormone level assessment to confirm the woman is not of child bearing potential must also be available as source documentation in the following cases:

1. Surgical bilateral oophorectomy without a hysterectomy
2. Reported 12 months of natural (spontaneous) amenorrhea with an appropriate clinical profile.

In the absence of the above medical documentation, Follicle Stimulating Hormone (FSH) testing is required at screening/baseline.

8.4.5 Anaphylaxis assessment

An adjudication committee (AC) will be put in place to determine whether cases of hypersensitivity identified through a search algorithm based on the Standardized Medical dictionary for regulatory activities (MedDRA) Queries may represent cases of anaphylaxis. Further details regarding the AC will be documented in the AC charter. See [Section 10.2.3](#) for details.

8.4.6 Assessment of cardio-cerebrovascular events

An AC will be put in place to review all cases identified through a search algorithm based on the Standardized MedDRA Queries of cardio-cerebrovascular events. The clinical presentation and association of these events with pre-existing risk factors will be part of the assessment. See [Section 10.2.3](#) for details.

8.4.7 Assessment of neoplastic events

An AC will be put in place to review all cases identified through a search algorithm based on the Standardized MedDRA Queries of neoplastic events. The clinical presentation and association of these events with pre-existing risk factors will be part of the assessment. See [Section 10.2.3](#) for details.

8.4.8 Appropriateness of safety measurements

In addition to safety assessments that are standard in this population, the potential of selected biomarkers will be evaluated for monitoring subjects' safety. Events of special interest such as anaphylaxis, malignancies, and cardio-cerebrovascular events will be monitored and will be adjudicated by expert ACs.

8.5 Additional assessments

[REDACTED]

The image consists of a series of horizontal bars of varying lengths, rendered in black on a white background. The bars are positioned in a grid-like pattern. At the top, there is a large black block that obscures the first few rows. Below this, the bars are visible, with some having white spaces and small white marks at their ends. The middle section of the image is mostly black, with only a few white marks visible. At the bottom, there is another large black block that obscures the last few rows. The overall effect is one of a heavily redacted or censored document.

10.1007/s00332-017-9160-2

[REDACTED]

8.5.3 Anti-ligelizumab antibody in serum

The presence of anti-ligelizumab antibodies will be assayed using a 3-tiered testing strategy consisting of a screening assay, a confirmatory assay and a titration of anti-ligelizumab responses by a titration assay for samples confirmed positive. A specific assay will be used to determine if ADAs are neutralizing in nature.

The detailed method to assess immunogenicity will be described in the bioanalytical raw data of the study and in the bioanalytical data report.

[REDACTED]

[REDACTED]

[REDACTED]

[REDACTED]

[REDACTED]

[REDACTED]

9 Study discontinuation and completion

9.1 Discontinuation

9.1.1 Discontinuation of study treatment

Discontinuation of investigational treatment for a subject occurs when investigational treatment is stopped earlier than the protocol planned duration, and can be initiated by either the subject or the investigator.

The investigator must discontinue investigational treatment for a given subject if, he/she believes that continuation would negatively impact the subject's well-being.

Investigational treatment must be discontinued under the following circumstances :

- Subject decision
- Adverse events for which continued exposure to the study drug would be detrimental
- Abnormal renal laboratory results requiring discontinuation (see [Section 16.3](#) Appendix 3)
- Abnormal liver laboratory results requiring discontinuation (see [Section 16.2](#) Appendix 2)
- Platelets < 75,000/ μ L

- Pregnancy (See [Section 8.4.4](#) and [Section 10.1.4](#))
- Subject develops a medical condition that requires use of prohibited treatment as per [Section 6.2.2](#), or if subject exhibits a behavior of non-compliance regarding prohibited medications
- Subject received a live virus vaccination during the study
- Subject experiences an unexpected hypersensitivity reaction of grade 5, as defined by the World Allergy Organization Grading System ([Cox et al 2017](#)), see [Section 16.6](#) Appendix 6:
 - Lower or upper respiratory: Respiratory failure with or without loss of consciousness; or
 - Cardiovascular: Hypotension with or without loss of consciousness
- Emergency use of epinephrine due to anaphylactic or anaphylactoid reaction
- Any other protocol deviation that results in a significant risk to the subject's safety
- Any situation in which study participation might result in a safety risk to the subject
- If a subject uses rescue oral corticosteroids for CSU more than 3 doses in a 30 day period or more than 9 doses of in total after week 12 during the study period (including the follow-up period).

If discontinuation of investigational treatment occurs, the investigator should make a reasonable effort to understand the primary reason for the subject's premature discontinuation of study treatment and record this information. Always consider reasons which are related to safety and efficacy first.

Subjects who discontinue investigational treatment or who decide they do not wish to participate in the study further should NOT be considered withdrawn from the study UNLESS they withdraw their consent (see [Section 9.1.2](#), withdrawal of informed consent). They will be expected to perform the Wk 52/Visit 240/EoT/TD assessments 4 weeks after their last dose and will be expected to perform all follow-up assessments (Visits 310-1999). If they fail to return for these assessments for unknown reasons, every effort (e.g. telephone, e-mail, letter) should be made to contact the subject/pre-designated contact as specified in the lost to follow-up section. This contact should preferably be done according to the study visit schedule.

At the final visit, all dispensed investigational product should be reconciled and the adverse event and concomitant medications reconciled on the appropriate eCRF.

If subjects discontinue from investigational treatment and are administered Xolair® (omalizumab) in the follow-up period, the subject should be discontinued from the study and no efficacy or safety assessments should be collected from the subject at the EOS visit.

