6.2.2 Prohibited medication

Use of the class of treatments displayed in [Table 6-2](#) is NOT allowed after start of screening. The minimum required period without prohibited treatment before Visit 1 is also listed in [Table 6-2](#). Each concomitant medication must be individually assessed against all exclusion criteria and the table below to see if it is allowed. If in doubt, the investigator should contact Novartis medical monitor or delegate before entering a subject to treatment period or allowing a new medication to be started.

Table 6-2 Prohibited medication

Medication	Minimum required period without medications
Omalizumab	4 months prior to Visit 1
Ligelizumab	No prior use allowed
Routine (more than 3 doses over a 5 day period) oral corticosteroids*	30 days prior to Visit 1
IV/IM/IA corticosteroids	30 days prior to Visit 1
Beta-blocker therapy	7 days prior to Visit 1
Leukotriene antagonists	Stop at Visit 1
H2-antihistamines	Stop at Visit 1
First generation H1-antihistamines	Stop at Visit 1
Hydroxychloroquine or chloroquine	30 days prior to Visit 1
Other immunosuppressive medication with or without known effect on CSU including but not limited to Methotrexate, cyclosporine A, cyclophosphamide, tacrolimus and mycophenolate mofetil	30 days prior to Visit 1
Intravenous immunoglobulin G	30 days prior to Visit 1

Medication	Minimum required period without medications
Plasmapheresis	30 days prior to Visit 1
Regular (daily or every other day) doxepin (oral)	14 days prior to Visit 1
Vaccination with inactivated viruses	48 hours prior to each dosing visit (i.e. Visit 110 to Visit 230)
Live attenuated vaccine	30 days prior to Visit 1
[REDACTED]	[REDACTED]

* Allowed only as rescue therapy only after Week12, on an as-needed basis for unbearable symptoms as per [Section 6.2.3](#). Other preparations of CS with limited systemic exposure for non-CSU indications can be used (e.g. Intra nasal or topical CS) as needed basis.

If the prohibited treatment was used during the study for any indication, the subject must discontinue use of the prohibited treatment if he/she wishes to continue in the study. If the subject received a live virus vaccination during the study, the subject must discontinue study treatment.

If a subject takes concomitant omalizumab (outside of study assigned tr [REDACTED] in the follow-up phase, the subject must discontinue from the study, in which case [REDACTED] ADA samples should not be collected at the End of Study (EoS) visit.

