8.4 Safety

Main safety and tolerability assessments include:

- AEs and SAEs, including AEs leading to treatment discontinuation and events of interest such as injection site reactions, anaphylaxis, pre-malignancy/malignancy, cardio-cerebrovascular events
- Physical examination
- Vital signs
- Laboratory evaluations
- ECG (Electrocardiogram)

Table 8-9 Assessments & Specifications

Assessment	Specification
Physical examination	
A complete physical examination will include the examination of general appearance, skin, neck (including thyroid), eyes, ears, nose, throat, lungs, heart, abdomen, back, lymph nodes, and extremities and vascular and neurological systems. If indicated based on medical history and/or symptoms, rectal, external genitalia, breast, and pelvic exams will be performed.
 
A short physical exam will include the examination of general appearance and vital signs. A short physical exam will be conducted at all visits starting from Visit 1 except where a complete physical examination is required (see Table 8-1). Information for all physical examinations must be included in the source documentation at the study site. Clinically relevant findings that are present prior to signing informed consent must be recorded on the appropriate eCRF that captures medical history.
 
Significant findings made after signing the informed consent which meet the definition of an Adverse Event must be recorded as an Adverse Event.

Vital signs	
Vital signs include blood pressure and pulse measurements. After the subject has been sitting for 5 minutes, with back supported and both feet placed on the floor, systolic and diastolic blood pressure will be measured 3 times using an automated validated device with an appropriately sized cuff. The repeat sitting measurements will be made at 1 – 2 minute intervals and the mean of the 3 measurements will be used. In case the cuff sizes available are not large enough for the subject's arm circumference, a sphygmomanometer with an appropriately sized cuff may be used.
 
Clinically notable vital signs are defined in Section 16.1 Appendix 1.

Height and weight	Height in centimeters (cm) and body weight (to the nearest 0.1 kilogram (kg) in indoor clothing, but without shoes) will be measured as specified in Table 8-1 .

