10.1.3 SAE reporting

To ensure subject safety, every SAE, regardless of causality, occurring after the subject has provided informed consent and until 30 days after the last study visit must be reported to Novartis safety within 24 hours of learning of its occurrence. Any SAEs experienced after the 30 day period after the last study visit should only be reported to Novartis Safety if the investigator suspects a causal relationship to study treatment. Any SAEs reported up to the subject's last visit will be reported in the eCRF. SAEs beyond that date will only be recorded in the Novartis Safety database.

Recurrent episodes, complications, or progression of the initial SAE must be reported as follow-up to the original episode, regardless of when the event occurs. This report must be submitted within 24 hours of the investigator receiving the follow-up information. An SAE that is considered completely unrelated to a previously reported one should be reported separately as a new event.

Information about all SAEs is collected and recorded on the Serious Adverse Event Report Form; all applicable sections of the form must be completed in order to provide a clinically thorough report. The Investigator must assess the relationship of each SAE to each specific component of the study treatment (if the study treatment consists of several components) complete the SAE Report Form in English and submit the completed form within 24 hours to Novartis. Detailed instructions regarding the submission process and requirements for signature are to be found in the investigator folder provided to each site.

Follow-up information is submitted as instructed in the investigator folder. Each reoccurrence, compilation, or progression of the original event must be reported as a follow-up to that event regardless of when it occurs. The follow-up information should describe whether the event has resolved or continues, if and how it was treated, whether the blind was broken or not, and whether the patient continued or withdrew from study participation.

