2.5.1 Primary endpoint

The primary variable is the number and percentage of patients who reported treatment emergent adverse events during the 64 week study period.

All adverse events which start after the first dose of study medication and within 16 weeks of the last dose will be considered as a treatment emergent adverse event.

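### Protocol 9.1.1 and 6.2.2 conflict on what is collected at the EoS visit after omalizumab in follow-up; read literally, 9.1.1 stops AE collection inside the 16-week TEAE window

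*Protocol*

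**What the plan says.** Two protocol sections cover omalizumab use in follow-up.

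- **Protocol 9.1.1.** The sentence opens "If subjects discontinue from investigational treatment and are administered Xolair", requires study discontinuation, and then says that "no efficacy or safety assessments should be collected from the subject at the EOS visit". The same section defines discontinuation as the case in which "investigational treatment is stopped earlier than the protocol planned duration". Just before the omalizumab sentence it asks that AEs and concomitant medications be reconciled at the final visit, and it makes no exception for omalizumab.
- **Protocol 6.2.2.** A subject who takes omalizumab "in the follow-up phase, the subject must discontinue from the study, in which case" (a redacted item follows) "ADA samples should not be collected at the End of Study (EoS) visit". The readable text says nothing against recording AEs, laboratory tests, vital signs or examinations.

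The surrounding rules are these.

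- Protocol 8.4 puts "AEs and SAEs, including AEs leading to treatment discontinuation" first in its list of safety assessments.
- Protocol 10.1.1 continues AE monitoring for at least 30 days after the last dose or the end-of-study visit, whichever is longer.
- Protocol 10.1.3 covers every SAE "occurring after the subject has provided informed consent and until 30 days after the last study visit must be reported". Protocol 10.1.4 makes every pregnancy after consent reportable.
- SAP 2.5.1: an event that starts after the first dose and "within 16 weeks of the last dose will be considered as a treatment emergent adverse event". Protocol 12.4.1 likewise counts onsets in follow-up.
- Protocol 12.4.3 and SAP 2.5.3 make no adjustment for discontinuation. SAP 2.7.1.1 ends exposure time at the first event, at treatment duration plus 16 weeks, or at Week 64, whichever is shortest. Study exit is not among these.

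**The concern.** A site whose subject stopped ligelizumab early and then started omalizumab has two instructions for one visit: collect no safety data, or collect everything except certain samples. The primary variable is TEAEs, and the visit lies inside the TEAE window. A site that follows 9.1.1 to the letter would not ask about AEs or run the safety tests planned for that visit, which include the end-of-study stool examination (parasitic infection is an AE of special interest in SAP 2.7.1.2).

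The effect has one direction. The subject stays in the Safety Set, so an event that is not recorded can only lower the crude incidence. The exposure-adjusted rate (EAIR) does not correct this, because its denominator keeps counting time after the subject has left. Early discontinuers are also not a random subset: protocol 9.1.1 includes those stopped for AEs, liver or renal abnormalities and low platelets.

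**Working it through.** **1. Is the visit inside the TEAE window?** Last dose: Day 337, Week 48 (protocol 3). Adding 16 weeks: 337 + 16 × 7 = 449, and 48 + 16 = 64. This reproduces the schedule (Visit 1999 at Day 449, Week 64), so the planned final visit is at the end of the window. Early discontinuers have their treatment-discontinuation visit 4 weeks after the last dose and then the three follow-up visits (9.1.1). At the usual 4-week spacing these fall 8, 12 and 16 weeks after the last dose. An exit visit before the last of these falls within the window.

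**2. The two sections side by side**

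| | 9.1.1 | 6.2.2 (readable text) |
|---|---|---|
| Who | Discontinued treatment, then omalizumab in follow-up | Any omalizumab use in follow-up |
| Study exit | Yes | Yes |
| Not collected at EoS | All efficacy and safety assessments | ADA samples and one redacted item |
| AEs at EoS | Barred, read with 8.4 | Not barred |

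They agree on study exit. They differ on one visit and on scope.

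**3. How many subjects?** The documents give no number. The literal 9.1.1 scope is bounded by expected dropout: 65 × 0.90 = 58.5, which protocol 12.8.1 gives as 58, so 65 − 58 = 7. The affected group is a subset of these. As an illustration of wider omalizumab use (all users under 6.2.2, or sites applying 9.1.1 to everyone) I also take 13 subjects, 20% of 65.

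**4. Effect on crude incidence.** One missed subject is 1/65 = 1.5 percentage points. It changes the overall figure only if the subject had no other TEAE, and a preferred-term figure only if it was the subject's first event of that term.

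**5. Person-time.** Planned total: 65 × 64 = 4,160 person-weeks. For *m* affected subjects, the part that depends on the exit visit is about 4*m* weeks (one visit interval). The part lost to study exit is at most 12*m* weeks (exit 4 weeks after the last dose).

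| *m* | Exit visit, 4*m* | Share | Study exit, 12*m* | Share |
|---|---|---|---|---|
| 1 | 4 | 0.10% | 12 | 0.29% |
| 6 | 24 | 0.58% | 72 | 1.73% |
| 7 | 28 | 0.67% | 84 | 2.02% |
| 13 | 52 | 1.25% | 156 | 3.75% |

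Dropouts contribute less than 64 weeks, so 4,160 is slightly too large. Counting only the 58 completers (58 × 64 = 3,712) gives ceilings for *m* = 7 of 28/3,712 = 0.75% and 84/3,712 = 2.26%.

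If the 30-day rule in 10.1.1 is applied after an exit 4 weeks post-dose, monitoring reaches day 28 + 30 = 58 of 112 and leaves 112 − 58 = 54 days uncovered.

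**6. EAIR.** Time after exit stays in the denominator, so at a constant event rate the EAIR is understated by about the last column: 0.29% for 1 subject, 2.02% for 7, 3.75% for 13.

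**7. Chance of missing a rare event.** Take the 3% event of protocol 12.8.1 and assume constant hazard over 64 weeks: λ = −ln(0.97)/64 = 0.000476 per week. The chance that at least one case falls in the uncaptured time is 1 − exp(−λ × weeks).

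- *m* = 1: 0.2% (4 weeks), 0.6% (12 weeks).
- *m* = 7: 1.3% (28 weeks), 3.9% (84 weeks).
- *m* = 13: 2.4% (52 weeks), 7.2% (156 weeks).

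**The case against.** The strongest reply is that 9.1.1 is loose wording inside a set of rules that already secures the data. SAEs and pregnancies are reportable with no omalizumab exception, AEs can be volunteered between visits, and AEs are to be reconciled at the final visit. Events after a switch to another anti-IgE antibody are also hard to attribute to ligelizumab, so not counting them is defensible. Two limits belong here as well: 6.2.2 is partly redacted, and the footnotes to Table 8-1 are not in the available text and may govern the EoS visit.

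Much of this stands, and it rules out several stronger readings that a reader might infer.

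- **That safety data are discarded.** Nothing already collected is removed, and every dosed subject stays in the Safety Set. The issue is non-collection at one visit.
- **That 9.1.1 costs 12 of the 16 post-dose weeks.** That time is lost through study exit, which 6.2.2 requires too. Copying the 6.2.2 wording into 9.1.1 would recover only the exit visit.
- **That SAEs and pregnancies go uncaptured.** Protocol 10.1.3 and 10.1.4 keep both reportable, although SAEs after the last visit enter only the safety database and not the eCRF.
- **That every subject who starts omalizumab falls under the 9.1.1 ban.** Read literally, it covers only those who stopped treatment early.
- **That 3 to 6 subjects (5% to 10% of 65) are affected.** On the literal scope this would need 3/7 = 43% to 6/7 = 86% of all expected dropouts to start omalizumab in follow-up. Nothing in the documents supports that.

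The reply does not remove the contradiction. The other rules do not override 9.1.1; they conflict with it, and a site cannot tell which to follow. Difficulty of attribution is a reason to label late events, and the SAP as written counts them without a label.

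**Conclusion.** The concern holds as a conflict between instructions, with a small, one-sided effect on the primary summary. Read literally, 9.1.1 bars AE collection at a visit within the TEAE window. This is contrary to the readable text of 6.2.2, to the reconciliation sentence in 9.1.1 itself and to the monitoring rule in 10.1.1.

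The likely gap is non-serious AEs and safety tests since the last regular visit. If all of the roughly 7 expected dropouts were affected, that is about 0.7% of planned person-time, and fewer is more likely. Separately, the SAP does not stop exposure time at study exit, which understates the EAIR by about 0.3% to 2% for 1 to 7 subjects and by up to 3.75% in the 13-subject illustration.

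These figures assume a constant event rate, exit no earlier than 4 weeks after the last dose, and numbers affected that the documents do not give. They do not show that a signal would be missed. The case for acting is that safety data are the purpose of the trial and the correction is cheap.

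**What to change.** **Protocol.** Reconcile 9.1.1 with 6.2.2, 10.1.1 and 10.1.3, and use one definition of the subjects covered. Withhold only the samples that omalizumab makes uninterpretable. State that AEs and concomitant medications, with the omalizumab start date, are still recorded at the exit/EoS visit. Check that the Table 8-1 footnotes agree. This concerns data collection only and takes no position on treatment or on study exit.

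**SAP.** Flag TEAEs with onset after omalizumab start, so that they can be shown with and without those events. In 2.7.1.1, add study exit as an end of exposure time when it comes before 16 weeks after the last dose.

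**Cost.** A protocol clarification, one flag and one censoring rule; the visit is already named in the schedule. The downside is a few late events confounded by omalizumab, which the flag handles. The change does not recover time after study exit, but the censoring rule keeps that time from being counted as observed.
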